In general, comparisons between measures with continuous variables (e.g., accuracy) within participants will be conducted using paired-tests, repeated-measures ANOVAs, and post-hoc t-tests as appropriate. Pearson correlations will be run between continuous variables (e.g., motor imagery accuracy and delta scores). Non-parametric tests will be used when assessments that with ordinal values (ICARS, KVIQ, mood, and cognitive ancillary measures) are included.

d. Early stopping rules. N/A

8. Risks

a. Medical risks, listing all procedures, their major and minor risks and expected frequency.

Risks/Benefits

The following relevant risk/benefit considerations and potential ethical issues may arise as part of the proposed study. Any adverse events will be promptly reported to the IRB. As this is not an intervention study, participants will be informed as part of the consent process that their medical care will not be affected or altered by their decision to participate in this research. There are no financial risks to the participant.

MRI: Screening of participants will consist of checks for contraindications to MRI scanning. Urine pregnancy testing will be conducted on-site for women of child bearing age. Currently pregnant participants will be excluded. There are no known significant risks for an MRI exam. Subjects, may, however, experience mild discomfort by the noise made by the magnet during the procedure, bothered by feelings of claustrophobia, or anxiety. There is a risk that the subject may become bored or fatigued with cognitive testing while in the scanner.

EMG: The EMG will be utilized to determine whether participants are moving their finger muscles during the imagery condition in the MRI scanner, in which they are not supposed to do so. To apply the surface electrodes on the participant's arm, skin prepping gel similar to a gentle exfoliating cream will first be applied and rubbed onto the participant's skin in order to remove any dead skin. There is a risk that subjects may not like the feeling of the cream or that their skin will become slightly irritated. The risks of the electrodes are the same as those of applying a band-aid on someone's arm: subjects may be uncomfortable with the adhesive feeling of the electrodes, and the electrodes might feel similar to ripping off a band-aid when taken off.

Incidental findings: Participants may feel anxious due to the outcome of the MRI examination if an abnormality is detected by the neuroradiologist. Female participants of child bearing age may become anxious if a pregnancy test screen is positive.

Behavioral testing: There is a risk that participants may become fatigued or bored while performing these tasks.

Mood and neurological assessments: Participants may feel uncomfortable or anxious while discussing their mood states with the study team. During the neurological exam, CA participants will be asked to stand, walk, and perform other motor functions while sitting, which may create a fall risk or sense of frustration if the participant has difficulty performing the tasks.

Confidentiality:

Despite all precautions, there is a very small risk that identifying information may be revealed. In addition to the study team, the IRB may access personal identifying information during routine monitoring.

b. Steps taken to minimize the risks.

MRI: Participants who report previous experiences of claustrophobia will also be excluded. All participants will be supplied with ear protection during MRI scanning to reduce noise exposure. If at any time the participant becomes fatigued during cognitive testing, they will have the opportunity to take a break or if needed discontinue the scan. To reduce the risk of dizziness and nausea, subjects will be instructed to enter and exit the MRI scanner slowly and to limit movement while in the MRI scanner.

EMG: To minimize the risk of any discomfort or skin irritation from the skin prepping gel, it will be applied carefully and gently to the subject's arm. It will be made sure that the participant is comfortable with the electrodes when they are put on, and care will be taken when they will be removed in order to minimize any discomfort and skin irritation. If the participant becomes uncomfortable during recording, then the electrodes can be removed early. If the participant has highly sensitive skin or would not like to go through with the EMG, then an EMG recording does not have to be obtained.

Incidental findings: All MRI structural scans will be read by a neuroradiologist within twoweeks of acquisition. In the event of an incidental finding, the PI and Co-I ([name]) will be contacted immediately. Participants will be contacted by the Co-I (or neuroradiologist, as determined by group discussion) to notify them of the findings via telephone. [name] can then refer the participant for follow-up care. Participants, upon written permission, may have the MRI findings sent to their primary care physician (PCP). Pregnancy test results will be delivered on the day of the MRI scan in person. If positive, study participation will end. If the participant is anxious or distraught from the test results, [name] will be on hand to assess the need for immediate or follow-up medical care and can refer accordingly. Behavioral testing: Prior to testing, participants will be reminded that study participation is voluntary and can be stopped at any time. Participants will receive ample opportunities to rest and take breaks as needed between tests.

Mood and neurological assessments: If the participant becomes anxious or upset while discussing mood states, the experimenter will take a break from questioning until the participant is ready to continue. The participant may discontinue at any time. If the participant exhibits signs of extreme duress, or is found to have severe depression or endorse suicidal ideation, we will involve [name] for consultation on the matter, engage their PCP, and/or escort them to the Emergency Department as appropriate. To minimize risk of falls during the neurological exam, we will have two experimenters present to assist with balance. If the participant or the experimenter decides that standing or walking will be too risky, that component of the neurological exam will be omitted.

Confidentiality:

• Subjects will be notified that they have passed or failed the screening directly in-person or by telephone. In the event of a screen failure, all documents containing the participant's personal health information will be destroyed. All participants will be assigned a code number to protect confidentiality in lieu of participant names. The code key which includes participant names will be kept separate from clinical data obtained such as MRI, neurological scores, and assessments. Names and contact information will be stored in a locked cabinet in [name] laboratory. Research staff that are IRB approved for this study will have access to this cabinet. Data will be stored on a secure REDCap database with password protections that will be accessible to study team members only. Publication of results will include only de-identified data.

Data Collected in the Study :

This research study will include outside collaborators for data analysis; however, this is not a multisite study. The collaborating site, led by [name] at Virginia Tech (VT) Fralin Biomedical Research Institute, will obtain an independent, non-overlapping IRB protocol for this project because of the separate and distinct protocols that will be carried out at each site. Participant recruitment, testing, and all data collection will occur solely at Johns Hopkins.

Defacing MRI data:

All study-related data containing PHI, including structural MRI data, will be securely transferred from the Kirby Center to Johns Hopkins OneDrive. On OneDrive, structural MRI data will be accessed by an IT-supported lab computer in the Psychiatric Neuroimaging Core to complete the defacing using Pydeface software. The software registers structural images to a custom template and uses the template space to remove all facial features from the structural MRI scan. Header editing software is used to identify header fields and remove all data from Dicom header fields containing PHI. Defacing and header stripping is verified using OsiriX MD Dicom viewer software. We will examine the de-faced images to ensure that the facial soft tissue has been removed successfully.

Defaced MRI data will be copied to Enterprise NAS for image processing and analysis.

Data Storage, Access, and Analysis:

Non-MRI related PHI and LDS data will remain on OneDrive and will be accessed via SafeDesktop. Additional LDS information will be stored on a JH IT-managed Network Attached Storage (NAS) via space allocated through the JHU Psychiatric Neuroimaging Core.

Data Sharing with Virginia Tech:

After verification, MRI and related data in the form of a limited data set (LDS), will be shared with non-Hopkins collaborators at VA Tech using a folder on OneDrive that is separate from the folder with PHI. LDS may include the date of birth, age in years or months, and date of MRI scan. [name] server is behind the VA Tech firewall and adheres to high PHI-protected security standards to safeguard data. We will share MRI and MRI-task behavioral data to VA Tech for analysis only. VA Tech may also be consulted during MRI scans to assist with technical errors for the real-time neurofeedback equipment; however, they will not be directly interacting with research subjects or learn their identity.

c. Plan for reporting unanticipated problems or study deviations.

In the event of an adverse event or serious adverse event that requires medical or professional intervention, the neurologist on the project, [name], will be available to assess the level of attention required for immediate medical care. This may consist of escort to the ED or referral for follow-up medical care with the participant's primary care physician or specialist. Furthermore, all events will be reported within 24 hours of the investigator becoming aware of the event to the IRB. Other unanticipated problems will be reported to the IRB within 2 weeks after the investigator becomes aware of the problem.

d. Legal risks such as the risks that would be associated with breach of confidentiality.

Every effort will be made to keep the information in the study confidential: (1) subjects will be assigned a code number and the code number only will be used to identify the scanning information, cognitive and behavioral information, or the clinical information that will be analyzed; (2) the computers on which the data will be stored are password protected on a secure server behind the Hopkins firewall; (3) written documents concerning the study will be kept in locked cabinets within locked personnel areas; (4) all personnel involved in the study have completed the appropriate HIPAA training and are fully aware of the need for confidentiality.

e. Financial risks to the participants.

These procedures will be performed at no cost to the subjects.

9. Benefits

a. Description of the probable benefits for the participant and for society.

Cerebellar ataxia participants may not directly benefit as a result of study participation. Data collected from this study may provide important future directions to improve protocols that could in turn benefit cerebellar ataxia patients in the future. Motor imagery, guided by rtfMRI-NF, may provide a novel, safe approach to "exercising" the motor circuitry and providing a new

rehabilitation tool for individuals with cerebellar ataxia. Moreover, this methodology may transfer to treatment for other movement disorders.

10. Payment and Remuneration

a. Detail compensation for participants including possible total compensation, proposed bonus, and any proposed reductions or penalties for not completing the protocol.

Participants will be given \$100 for completing the study. Participants will be paid by gift card at the end of the study. Participants will be provided a parking voucher at the first visit (East Baltimore campus).

If participants are from out of town, we may be able to provide one night of complimentary hotel lodging at Residence Inn Baltimore at the Johns Hopkins Medical Campus if needed, along with transportation to and from the hotel and our scanning facility if needed. Funds are limited and will be applied as needed but cannot be extended to all participants.

If a participant leaves the study early, or is dropped from the study by the principal investigator for not complying with the procedures listed in this consent form, he or she will only be paid for the parts of the study that he or she has completed. The study will not reimburse for, or replace, a gift card that has been lost, stolen, or expired.

11. Costs

a. Detail costs of study procedure(s) or drug (s) or substance(s) to participants and identify who will pay for them.

N/A

References

- 1. Morgan, O.P., et al., *The Cerebellum and Implicit Sequencing: Evidence from Cerebellar Ataxia*. The Cerebellum, 2020.
- 2. de Vries, S. and T. Mulder, *Motor imagery and stroke rehabilitation: a critical discussion*. J Rehabil Med, 2007. **39**(1): p. 5-13.
- 3. Holmes, G., *The Cerebellum of Man.* Brain, 1939. 62: p. 30.
- 4. Leggio, M.G., et al., *The neuropsychological profile of cerebellar damage: The sequencing hypothesis.* Cortex, 2011. **47**(1): p. 137-44.

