Aim 1: Use rtfMRI-NF and motor imagery to train CA participants to improve motor accuracy.

- Aim 1.1: Train CA participants (N=30) to engage neural regions during motor imagery that are associated with overt finger tapping at slow (1 Hz) and fast (4 Hz) speeds.
- *Aim 1.2:* Correlate motor imagery skill (i.e., slider bar distance from target) with overt tapping performance.

• *Aim 1.3:* Evaluate the relations between overt tapping accuracy and neurological symptoms as well as motor imagery skill with offline assessments of motor imagery ability.

Aim 1 will use rtfMRI-NF during motor imagery to train CA participants to improve motor accuracy. Thirty CA participants will receive NF during motor imagery in an experiment in which we hypothesize that 1) CA participants will be able to control a NF interface; 2) imagery skill will be positively correlated to improvements in overt tapping accuracy; and 3) overt tapping accuracy will correlate with neurological signs, whereas motor imagery skill will correlate with assessed motor imagery ability.

Aim 2: Translate rtfMRI-NF learning into at-home therapy strategies for continued training.

- Aim 2.1: Examine whether motor imagery strategies from rtfMRI-NF training translate into successful at-home therapy training
- *Aim 2.2:* Compare motor imagery performance during rtfMRI NF with at-home motor imagery benefits.

Aim 2 will translate rtfMRI-NF learning into at-home therapy strategies for three weeks of continued training in which we hypothesize that 1) continued practice with imagery strategies will lead to additional improvements in motor timing and precision, and 2) performance during rtfMRI-NF training will positively correlate with at-home motor imagery performance.

Exploratory

Aim 3: Design next-generation approaches to rtfMRI-NF. The data from Aim 1 will be analyzed to optimize the future rtfMRI experiments in the CA population. We will examine whether the NF session can be streamlined to deliver more accurate NF in shorter sessions. To enable future studies to operate within an experimental medicine frame work we will examine three major questions. Aim 3.1 Are there group differences in CA versus healthy controls? Aim 3.2 Are healthy models of motor imagery viable for CA participant NF? Aim 3.3 Can the NF session be streamlined to deliver more accurate NF in more efficient sessions?

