2) At-home overt tapping accuracy improvements will be analyzed by comparing the mean accuracy on overt tapping between baseline and final measures at home (pre- and post- 3-week at-home therapy training) to compute a delta measure that will indicate magnitude of accuracy improvement at each frequency (1 and 4 Hz). This will be analyzed using paired t-tests within frequency conditions. As a follow-up analysis of improvement during the 3-week therapy (for training Groups 2 and 3 who perform daily overt tapping exercises), the mean accuracy of overt tapping at both frequencies will be measured for each session and compared using repeated measures ANOVAs and post-hoc t-tests as appropriate.

b. Secondary outcome variables.

1) The relation between imagery accuracy and tapping accuracy with supplemental assessments of imagery and motor symptoms will be analyzed using non-parametric correlation tests, such as Spearman's rank-order correlation coefficient test, because of the ordinal values in the KVIQ and ICARS assessments. Mean imagery accuracy and tapping accuracy scores from the final MRI assessment will be compared separately to the KVIA an ICARS.

2) The relation between brain activity during imagery NF and overt tapping improvements will be analyzed using Pearson correlations between the mean of region of interest activity (minus rest) during NF training and the RSME delta scores.

3) The influence of ancillary measures on overt tapping and motor imagery accuracy will be analyzed using non-parametric correlation tests (e.g., Spearman's rank) because of the ordinal values in the HAM-A, HAM-D, CCAS, and WRAT assessments. Mean imagery accuracy and tapping accuracy scores from the final MRI assessment will be compared separately to each of the assessments.

c. Statistical plan including sample size justification and interim data analysis.

We plan to enroll 30 participants in this study. The sample size was determined through a power analyses using G*Power 3.1.9.2 software [40]. Because motor imagery, with or without rtfMRI-NF, has never been used as a treatment approach for people with cerebellar ataxia (CA), as proposed here, our power analyses are extrapolated from information we have obtained that in three prior studies that support the premise and feasibility of Aim 1, which is to use rtfMRI-NF and motor imagery to train CA participants to improve motor accuracy.

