In our third study, rtfMRI-NF was applied to healthy adults (N=17) while performing the overt tapping and imagery tasks proposed in Aim 1. Results revealed that several brain regions engaged during motor imagery positively correlated with RSME improvements: bilateral M1, right premotor cortex and the SMA. Atlas-based contrast values (motor imagery – rest) for these ROIs were computed. Entering into the model the correlation value and standard deviations between the mean contrast values per ROI and mean RSME "delta" revealed that **a** sample size of 17 - 22 participants yielded at least 81% power at the .05 level, one-tailed, to reject the null hypothesis of no linear relationship between motor imagery activation and RSME improvements.

Taken together, we propose to enroll N=30 CA participants into this study. This N will be overpowered for some aspects of the study, such as tapping accuracy. However, we are also taking into consideration that the rtfMRI-NF data was based on healthy controls, and we anticipate greater variability in rtfMRI-NF training in the CA participants. Moreover, a sample size of 30 will allow us some room to make additional comparisons with the at-home therapy data (Aim 2) and exploratory MRI data analyses (Aim 3).

Sample size may be underpowered for the some of the proposed comparisons across aims. The amount of motor imagery necessary to improve overt tapping performance in CA patients is unknown. We modeled our power analysis parameters to target Aim 1. However, we will compare the neuroimaging data with at-home therapy performance variables (Aim 2) and will use the data from Aim 1 to conduct exploratory analyses to improve future protocols (Aim 3). The current sample size may be too small to detect significant results on all comparisons. Nevertheless, we consider the data we collect here to be highly informative for future studies and will serve as pilot data (and power analyses) for future grant applications.

Statistical methods that will be used with respect to each outcome measure:

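### Aim 1 hypothesis 3 contrasts two relations, but the planned separate correlations cannot show that one is larger than the other

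*Combined protocol and SAP*

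**What the plan says.** Section 2 (Objectives) states the matter twice. The Aim 1.3 bullet is neutral: "Evaluate the relations between overt tapping accuracy and neurological symptoms as well as motor imagery skill with offline assessments of motor imagery ability". Hypothesis 3, in the paragraph that follows the bullets, sets the two relations against each other: "overt tapping accuracy will correlate with neurological signs, whereas motor imagery skill will correlate with assessed motor imagery ability".

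The matching analysis is section 7b, item 1. The relations "will be analyzed using non-parametric correlation tests, such as" Spearman's, and "Mean imagery accuracy and tapping accuracy scores from the final MRI assessment will be compared separately to the KVIA an ICARS" (KVIA is evidently the KVIQ). On the natural reading this gives four correlations: tapping with ICARS, imagery with KVIQ, and the two cross pairs, tapping with KVIQ and imagery with ICARS.

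The general methods at the end of section 7c add only this: "Non-parametric tests will be used when assessments that with ordinal values (ICARS, KVIQ, mood, and cognitive ancillary measures) are included". Section 7 contains no test or interval for a difference between two correlations, and no rule for reading the cross pairs. Sidedness for these correlations is not stated. On sample size, "we propose to enroll N=30 CA participants into this study".

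**The concern.** A *whereas* between two relations invites a comparative reading: motor severity goes with tapping more than with imagery, and imagery ability goes with imagery more than with tapping. Support for that is a statement about differences between correlations. A set of separate p-values does not supply it, because one correlation can be significant and another not when the true values are equal. Equally, both predicted correlations can be significant while the cross pairs are just as strong.

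Equal correlations are a realistic possibility here. Section 3 says that the feedback classifier is trained on each person's own activity during a simple motor task such as tapping, and Aim 1.2 sets out to correlate imagery skill with tapping performance. One underlying severity factor could drive both scores. Section 7c says the data will feed later grant applications and power analyses, so a claim of specificity that the analysis cannot support could be carried forward.

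**Working it through.** **The plan's own figure.** The only power statement for a correlation (section 7c, third study) is that "17 - 22 participants yielded at least 81% power at the .05 level, one-tailed". It concerns imagery-related brain activation and tapping improvement in healthy adults, not ICARS or KVIQ, and the correlation used is not printed. It can only be inverted. With Fisher's z, atanh(r) = (0.878 + 1.645)/√(n − 3), where 0.878 and 1.645 are the normal quantiles for 81% power and one-tailed 0.05:
- n = 17: 2.523/√14 = 0.674, so r = 0.59.
- n = 22: 2.523/√19 = 0.579, so r = 0.52.

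Nothing is stated for Aim 1.3 or for a difference between correlations.

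**Inputs.** N = 30 comes from section 7c and Spearman from 7b item 1. Assumed, because the documents do not give them: two-sided 0.05, normal underlying variables, all true correlations, and all scores aligned in sign.

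**Threshold for one correlation.** t(0.975, 28) = 2.048, so |rho| must exceed 2.048/√(28 + 2.048²) = 0.361.

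**Why separate tests mislead: one example.** Suppose rho(tapping, ICARS) = 0.40, rho(imagery, ICARS) = 0.32 and rho(tapping, imagery) = 0.30. The first passes 0.361 and the second does not. The Meng-Rosenthal-Rubin test of their difference gives:
- mean squared correlation = (0.16 + 0.1024)/2 = 0.1312
- f = 0.70/(2 × 0.8688) = 0.403
- h = (1 − 0.403 × 0.1312)/0.8688 = 1.090
- z = (0.4236 − 0.3316) × √(27/(2 × 0.70 × 1.090)) = 0.0920 × 4.21 = 0.39, p about 0.70

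The split appears, yet there is no evidence of a difference.

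**How often this happens when no specificity exists.** Simulation, 20,000 trials per setting, all four true correlations equal; ICARS–KVIQ correlation varied from 0 to 0.4; direct test is Dunn-Clark z.

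| Common rho | Tapping–imagery | Tapping–ICARS significant, imagery–ICARS not | Full four-way split | Both predicted significant | Direct test falsely significant |
|---|---|---|---|---|---|
| 0.3 | 0.2 | 20–21% | 3–5% | 12% | 5–6% |
| 0.4 | 0.2 | 23% | 4–8% | 32–33% | 6% |
| 0.4 | 0.4 | 20% | 3–5% | 31–33% | 6% |
| 0.5 | 0.3 | 16% | 3–5% | 61–62% | 6% |

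A stronger tapping–imagery correlation lowers the one-scale figure: about 14% when it is 0.5 and the common rho is 0.5.

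**What the direct test can deliver at N = 30.**
- 0.5 versus 0: power 47%, about 56% and 62% when tapping and imagery correlate 0, 0.2 and 0.3.
- 0.5 versus 0.2 (tapping–imagery 0.3): about 27%.
- 0.6 versus 0 (tapping–imagery 0.3): 82%.

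Approximate N for 80% power is 3 + (1.96 + 0.8416)² × 2(1 − r₁₂)h/(atanh r₁ − atanh r₂)², where r₁₂ is the tapping–imagery correlation. With r₁₂ = 0.3:
- 0.5 versus 0: 3 + 7.849 × 1.4 × 1.086/0.302 = 43 (rounded up).
- 0.5 versus 0.2: 3 + 7.849 × 1.4 × 1.100/0.120 = 104 (rounded up, from unrounded terms).

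**The case against.** The strongest reply is that no dissociation is promised. The Aim 1.3 bullet names two relations and asks only that they be evaluated. Hypothesis 3 pairs each score with its own scale and never says that the cross pairs should be smaller or absent. Read as two stand-alone predictions, it is fully answered by the planned Spearman tests. This stands as a fair reading, and it is why the point is about interpretation. But the wording also allows the comparative reading, item 1 appears to produce the cross pairs that invite it, and nothing in the plan tells the analyst which claim the results may support.

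The second reply concerns size, and it also stands. A reader might count every trial in which exactly one of the two ICARS correlations is significant, which is 32% to 46% in these settings. About half of those run opposite to the prediction and would not be taken as support. A reader might also take the one-scale figure of 16% to 23% as the chance of falsely showing the whole pattern. The full split needs the KVIQ half too and arises in only about 3% to 8%.

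Third, a reader might infer that Aim 1.3 will be used to argue that imagery is a route around motor impairment. No section says so. Section 3 notes that the method can be used when movement is severely limited, but does not rest that on these correlations.

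Finally, the analysis is secondary, section 7c admits that the sample may be too small for some comparisons, and a direct test will often be inconclusive. True, but that caveat concerns missed effects. The risk here is a positive claim of specificity without a test of it.

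**Conclusion.** The point holds in a limited form. Separate correlations answer whether each relation exists. They do not show that either is stronger than its cross pair, which is what the contrast in hypothesis 3 suggests. The more likely ways to over-read the results are a chance split on one scale, or two significant predicted correlations with equally strong cross pairs. A chance split across both scales is uncommon.

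All the sizes depend on assumed true correlations, two-sided 0.05 and approximate normality, none of which the documents state for this aim. The analysis is listed as secondary and the paired t-tests of section 7a are untouched. A modest change to the analysis wording is warranted; no change to the design is.

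**What to change.** In section 7b item 1:
1. Align signs first. RSME, slider distance and ICARS rise with worse performance, and KVIQ rises with better imagery.
2. Prespecify two differences: rho(tapping, ICARS) minus rho(imagery, ICARS), and rho(imagery, KVIQ) minus rho(tapping, KVIQ). Give each a bootstrap interval that resamples participants, or a Steiger or Dunn-Clark test for dependent correlations. State the sidedness.
3. Label these as estimates. Claim specificity for a scale only where its interval excludes zero. Otherwise report the correlations as separate predictions with no specificity claim.

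If the investigators intend only two separate predictions, rewording hypothesis 3 to drop the contrast is a sufficient alternative.

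The cost is a few lines of text and two extra computations on data already being collected. The downside is low power: at N=30 the result will often be that specificity is not established, unless the true gap is about 0.6.
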